Study Duration	
Anticipated enrollment of the first subject: March 2018
 
Anticipated enrollment of the last subject: December 2018
 
Anticipated study completion date: December 2019

Procedures of the Trial

Item	Screening Period			Treatment Period (28 days/cycle)			Post-Treatment		Survival Follow-Up
	Within 3 weeks before dosing	Within 1 week before dosing	Cycle 1		Cycles 2–26				Every 1 month (± 3 d)
			Day 1	Day 15	Day 1	Day 15			
				(± 3 d)	(± 3 d)	(± 3 d)	End of Treatment/Withdrawal (+3d)	End of Treatment Visit (± 3 d)	
Baseline Data									
Informed consent	×								
Demographics	×								
Tumor history	×								
Past medical history ^[1]									
Concomitant medication ^[2]	×	×	×						
History of alcoholism	×								
Laboratory Test									
Hematology ^[3]		×		×	×	×	×	×	
Blood biochemistry ^[4]		×		×	×	×	×	×	
Urinalysis ^[5]		×		×	×	×	×	×	
Routine stool test ^[6]		×		×	×		×		
Coagulation function test ^[7]		×		×	×		×		

Compound Code: SHR-1210
Protocol No.: SHR-1210-APTN-II-208-HCC
Final Version 3.0, 29 May, 2019

Item	Screening Period			Treatment Period (28 days/cycle)			Post-Treatment		Survival Follow-Up
	Within 3 weeks before dosing	Within 1 week before dosing	Cycle 1		Cycles 2–26				Every 1 month (± 3 d)
			Day 1	Day 15	Day 1	Day 15	End of Treatment/Withdrawal (+3d)	End of Treatment Visit (± 3 d)	
				(± 3 d)	(± 3 d)	(± 3 d)			
Thyroid function test ^[8]	×				×		×		
Alpha-fetoprotein		×	× (D1 ± 7 d every 2nd cycle)				×		
Examination of hepatitis B and hepatitis C ^[9]	×		× (D1 ± 7 d every 2nd cycle)				×		
Pregnancy test ¹⁰		×					×		
Myocardial zymogram ^[11]		×					×		
Pituitary adrenal axis test ^[12]	×								
HIV test	×								
Clinical Evaluation and Examination									
Adverse event ^[13]	From informed consent to 30 days after the last dose								
Vital signs ^[14]		×	×	×	×	×	×	×	
Physical examination ^[15]		×	×	×	×	×	×	×	
ECOG PS		×			×		×	×	
ECG ^[16]		×		×	×		×		
Echocardiography ^[17]		×					×		

Item	Screening Period			Treatment Period (28 days/cycle)			Post-Treatment		Survival Follow-Up
	Within 3 weeks before dosing	Within 1 week before dosing	Cycle 1		Cycles 2–26		End of Treatment/Withdrawal (+3d)	End of Treatment Visit (± 3 d)	Every 1 month (± 3 d)
			Day 1	Day 15	Day 1	Day 15			
				(± 3 d)	(± 3 d)	(± 3 d)			
Blood pressure monitoring ^[18]	×	×		×	×	×	×		
Investigational Drug									
Administration of SHR-1210 ^[19]			×	×	×	×			

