#### **Study day**

The date of first administration is defined as the starting date of the study (Day 1) and the starting date of the study as the basis. The study days corresponding to the examination or event are calculated according to the following formula:

- If the examination/event date is prior to the starting date of the study, the study days = the examination date - the starting date of the study;
- If the examination/event date is on or after the starting date of the study, the study days = the examination date - the starting date of the study + 1.

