**Table 1. Derived variables of SHR-1210 and Apatinib**

Variable	SHR-1210	Apatinib
Protocol-specified method of administration	Administration once per two weeks, 200 mg or 3 mg/kg each time, and every 4 weeks for a cycle	Administration once per day, 250 mg each time, and every 4 weeks for a cycle
Duration of drug exposure (days)	Date of last administration - date of first administration + 14	Date of last administration - date of first administration + 1
Planned duration of treatment (days)	Date of last administration - date of first administration + 14	Date of last administration - date of first administration + 1
Cycle length (weeks)	Except for the last cycle: (Actual starting date of next cycle - 1 - actual starting date of the cycle + 1) / 7; Last cycle: (Date of last administration + 14 - actual starting date of the cycle) / 7	Except for the last cycle: (Actual starting date of next cycle - 1 - actual starting date of the cycle + 1) / 7; Last cycle: (Date of last administration + 1 - actual starting date of the cycle) / 7
Actual cumulative dose per cycle (mg)	Actual administration dose (mg) during a cycle is summarized, and each actual administration dose is recorded in CRF	
Actual cumulative doses of all cycles (mg)	Actual administration doses (mg) during all cycles are summarized	
Planned cumulative dose per cycle (mg)	200 (mg) × 2 = 400 (mg)*	250 (mg) × 28 = 7000 (mg)*
Actual dose intensity per cycle (mg/4-week cycle)	Actual cumulative dose per cycle (mg) / [cycle length (weeks) / 4]	
Actual dose intensity (mg/4-week cycle)	Actual cumulative doses of all cycles (mg) / [planned treatment time (weeks) / 4]	
Planned dose intensity per cycle (mg/4-week cycle)	Planned cumulative dose per cycle (mg) / [1 (4-week cycle)] = 400 (mg/4-week cycle)**	Planned cumulative dose per cycle (mg) / [1 (4-week cycle)] = 7000 (mg/4-week cycle)
Planned dose intensity (mg/4-week cycle)	400 (mg/4-week cycle)***	7000 (mg/4-week cycle)
Relative dose intensity per cycle (%)	100 × [Actual dose intensity per cycle (mg/4-week cycle)] / [Planned dose intensity per cycle (mg/4-week cycle)]	
Relative dose intensity (%)	100 × [Actual dose intensity (mg/4-week cycle)] / [Planned dose intensity (mg/4-week cycle)]	

\*: If the baseline weight of the subject is < 50 kg, the planned cumulative dose per cycle (mg) = 3 (mg/kg) × baseline weight (kg) × 2 = 6 × baseline weight (mg);

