The selected AEs are analyzed separately. For each selected AE, the time to first event (weeks) is summarized in the form of continuous variables, that is, mean, standard deviation, median, maximum, minimum, and quartile (Q1 and Q3) are used for the summary. The greatest grade and the measures taken to study drugs are summarized in the form of categorical variables. The events are also summarized according to factors such as TEAE severity and TEAE occurrence cycle, respectively. The number and percentage of subjects who experience each selected AE and have been resolved are summarized.

The calculation method for the cycle length of TEAE which occurs is:

(Starting date of TEAE - date of first administration + 1) / 28 + 1, and the integer part will be retained;

Time to first event (weeks) = (date of first event occurrence - date of first administration + 1) / 7.

All AEs will be listed. Treatment-related AEs, AEs that result in treatment termination, AEs that result in treatment delay or dose reduction, and death will be listed separately.

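### The SAP formula for the cycle of TEAE onset puts the last day of each nominal 28-day cycle into the next cycle

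*SAP*

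**What the plan says.** SAP section 5.5.2 analyses the selected adverse events separately and adds that "The events are also summarized according to factors such as TEAE severity and TEAE occurrence cycle, respectively". The onset cycle is derived as "Starting date of TEAE - date of first administration + 1) / 28 + 1, and the integer part will be retained". The SAP's label for this quantity speaks of a cycle length, but the sentence on occurrence cycle shows that the cycle number at onset is meant.

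Three other places fix how days and cycles are counted:

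- **Day numbering.** In SAP section 5.1.2, under Study day, "The date of first administration is defined as the starting date of the study (Day 1"). On or after that date, "the study days = the examination date - the starting date of the study + 1". There is no Day 0.
- **Cycle length.** The Protocol's schedule of procedures is headed "Treatment Period (28 days/cycle") and runs to Cycle 26. SAP Table 1 also uses a 4-week cycle: "Administration once per two weeks, 200 mg or 3 mg/kg each time, and every 4 weeks for a cycle".
- **Cycle boundaries for exposure.** For all but the last cycle, SAP Table 1 computes the length in weeks as ("Actual starting date of next cycle - 1 - actual starting date of the cycle + 1) / 7". A cycle therefore ends on the day before the next one starts.

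**The concern.** The formula adds 1 twice. The inner + 1 turns a date difference into a study day that starts at 1. The outer + 1 turns a count of completed 28-day blocks into a cycle number that starts at 1. The outer term needs a block count that starts from 0, and the inner term spoils this. Once the result is truncated, any study day that is an exact multiple of 28 moves up one cycle.

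What is at stake is the by-cycle table of selected TEAEs. The error runs in one direction only: it takes events out of the earlier cycle and makes onset look slightly later. Because the derivation is prespecified, a programmer who follows it literally reproduces the error, and one who quietly corrects it departs from the SAP.

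**Working it through.** The documents report no figure from this formula, so the check evaluates it directly.

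**Inputs**

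- First dose is Day 1, and study day d = date − first dose date + 1 (SAP 5.1.2).
- A cycle is 28 days (Protocol schedule; SAP Table 1), so nominal Cycle 1 is Days 1–28 and Cycle 2 starts on Day 29.
- The schedule covers 26 cycles: 26 × 28 = 728 days.

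**Formulas**

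- SAP: cycle = integer part of (d/28 + 1), because the bracket in the SAP formula is d.
- Nominal cycle: integer part of ((d − 1)/28) + 1.

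**Results around the boundaries**

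| Study day d | d/28 + 1 | SAP cycle | Nominal cycle |
|---|---|---|---|
| 1 | 1.036 | 1 | 1 |
| 27 | 1.964 | 1 | 1 |
| 28 | 2.000 | **2** | 1 |
| 29 | 2.036 | 2 | 2 |
| 55 | 2.964 | 2 | 2 |
| 56 | 3.000 | **3** | 2 |
| 57 | 3.036 | 3 | 3 |
| 728 | 27.000 | **27** | 26 |

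Truncating before or after the outer + 1 gives the same answer, so the order of operations does not matter.

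**All days from 1 to 728.** There are 26 mismatches, one per cycle. Every one falls on a multiple of 28 and every one is exactly one cycle too high. The share is 26/728 = 1/28 = 3.6% of study days. Under the SAP formula Cycle 1 holds 27 days (1–27). Day 728 goes to a Cycle 27, although the schedule stops at Cycle 26.

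**Consistency within the SAP.** With Cycle 2 starting on Day 29, Table 1 gives Cycle 1 a length of (29 − 1 − 1 + 1)/7 = 28/7 = 4 weeks, so Day 28 belongs to Cycle 1. The time-to-first-event formula in 5.5.2 has the same + 1 in its numerator, but it is not truncated to a cycle number and the term does no harm there. A Day 28 event would thus be reported at 28/7 = 4.0 weeks and yet be counted in Cycle 2 of a 4-week schedule.

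**Check of the correction.** Without the inner + 1, the integer part of ((d − 1)/28 + 1) matches the nominal cycle on all 728 days. Rounding d/28 up to the next integer does the same.

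**The case against.** The strongest objection is that real cycles drift. Day 1 of Cycle 2 and later has a ±3-day window, and SAP Table 1 bounds cycles by their actual start dates. If Cycle 2 starts early, on study day 26, then Day 28 lies in actual Cycle 2: the SAP formula happens to be right and the corrected one returns Cycle 1. If Cycle 2 starts late, on study day 31, Days 29 and 30 lie in actual Cycle 1 and both formulas return Cycle 2.

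This stands as a limitation of any fixed 28-day count, and it means the error is exact only for nominal cycles. It does not rescue the formula, which itself counts fixed 28-day blocks from the first dose and misplaces the boundary on those terms. Protocol section 6 also keeps examinations and procedures to the time schedule regardless of drug interruption, which favours nominal counting.

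The second objection is that the consequence is very small, and this is accepted. The variable feeds one descriptive breakdown with no test or threshold. Incidence is counted by subject, time to first event has its own formula, and all adverse events are listed. Partly missing onset dates are imputed (SAP 5.1.6.1), so some onset days are approximate anyway. The documents give no distribution of onset days. Protocol section 5.1.5 requires examinations within 72 hours before each dose, so some clustering just before a visit is possible, but it cannot be quantified. Findings made on nominal Day 29 itself are assigned correctly.

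**Conclusion.** The concern holds. Against nominal 28-day cycles counted from the first dose, the formula assigns the last day of every cycle to the next one, and nothing else in the SAP or Protocol corrects this. The affected share is 1 onset day in 28. Reading that as about 3.6% of events assumes that onset is spread evenly over the cycle. The shift is always one cycle later.

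This is a minor point. It affects the by-cycle summary of selected TEAEs only and leaves other safety results, the ORR decision rule and the other efficacy analyses unchanged.

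**What to change.** In SAP section 5.5.2, replace the derivation with: the integer part of (TEAE start date − date of first administration)/28 + 1. The label should also say cycle of onset rather than cycle length.

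It would help to add a sentence that the table uses nominal 28-day cycles from the first dose, since Table 1 uses actual cycle dates for exposure and the correction does not align the two.

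The cost is one line of SAP text and one line of code, plus the optional sentence. Trial conduct, data collection and other analyses do not change.

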### 5.5.3. Laboratory evaluations

Baseline laboratory test is defined as the latest non-missing test result prior to the first dose of the study drugs.

The worst grades (normal, abnormal without clinical significance, and abnormal with clinical significance) of baseline and post-baseline laboratory tests in hematology, blood biochemistry, blood lipase, blood amylase, urinalysis, stool routine, coagulation function test, thyroid function test, myocardial zymogram, pituitary adrenal axis test, and alpha fetoprotein are summarized by using shift table. The post-baseline measurements of each subject are summarized according to the worst severity grades. Severity, in descending order: Abnormal with clinical significance, abnormal without clinical significance, normal, and not examined. For continuous variables, the laboratory tests and changes from baseline values will be summarized by scheduled time point using descriptive statistics, such as number of subjects (n), arithmetic mean, standard deviation (SD), median, minimum (Min), and maximum (Max).

All laboratory measurements will be listed by subject ID, among which, abnormal values will be marked with H/L and indicated for clinical significance if any.

Virological examination and pregnancy test results will be listed.

Unplanned single test result will be listed.

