2.2.2. Secondary endpoints

Efficacy:

- Objective response rate as assessed by investigator as per RECIST 1.1;
- Progression-free survival (PFS)
- Time to response
- Duration of response
- Disease control rate (DCR)
- 9-month overall survival rate (9-month OS%)
- 12-month overall survival rate (12-month OS%)
- Overall survival
- ORR, PFS, DOR, and DCR as assessed by IRC as per mRECIST criteria.

Safety:

- Incidences and severities of adverse events (AEs) and serious adverse events (SAEs), laboratory abnormalities, as per NCI-CTCAE v4.03;
- Incidence of AEs resulting in dose interruption and discontinuation;

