Grade of Liver Function Test Increased (NCI CTCAE V4)	Treatment	Follow-up
Grade 1 AST or ALT > ULN-3.0 × ULN and/or T.bili>ULN-1.5 × ULN	
 Continue I-O treatment according to the study protocol 	
 Continue hepatic function monitoring as per study protocol If it is aggravated: Provide treatment according to the method for Grade 2 or Grade 3/4 situations
Grade 2 AST or ALT ≥ 3.0 to ≤ 5 × ULN and/or T.bili > 1.5 to ≤ 3 × ULN	
 Delay I-O treatment according to the study protocol Increase the monitoring frequency to once every 3 days 	
If improving to baseline level:
 
 Resume routine monitoring and resume I-O treatment according to the study protocol 
If the increase lasts for > 5-7 days or becomes aggravated:
 
 Intravenous administration of 0.5-1mg/kg/day methylprednisolone or an equivalent orally administrated dose. If LFT returns to grade 1 or baseline, reduce the dose of steroids for at least 1 month and consider prophylactic antibiotics to prevent opportunistic infections, and then resume I-O treatment according to the study protocol
Grade 3 - 4 AST or ALT > 5×ULN and/or T.bili>3×ULN	
 Terminate I-O treatment* Increase the monitoring frequency to once every 1-2 days Intravenous administration of 1.0-2.0mg/kg/day methylprednisolone or an equivalent dose via intravenous injection** Add prophylactic antibiotics to prevent opportunistic infections Consultation with the gastroenterology department 	
If it returns to Grade 2:
 
 Reduce the dose of steroids for at least 1 month 
If there is no improvement within >3-5 days, or if the symptoms are aggravated or deteriorated:
 
 Add 1 g of mycophenolate mofetil, b.i.d If the symptoms are not relieved within 3-5 days, consider other immunosuppressants based on local guidelines

[figure not shown]
If subjects receiving intravenous injection of steroids show continuous clinical improvements, it is allowed, at the start of dose tapering or earlier, to switch to oral administration of corticosteroids (such as prednisone) at equivalent dose. When switching to oral corticosteroids with an equivalent dose, it should be considered that the bioavailability of oral corticosteroids is relatively low.

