### 5.5.2. Adverse events

All AEs are encoded by using MedDRA v24.0 and graded using NCI-CTCAE v4.03. For the same SOC and/or PT, multiple cases of the same events occurred in one subject will be counted only once. For the same AE reported in one subject multiple times but varying in CTCAE grade, the AE of the greatest grade will be enumerated.

Treatment-emergent adverse events (TEAEs) are defined as any adverse events (AEs) that are new or worse than those at baseline (before treatment) after initiation of the study drugs. Only TEAEs will be summarized, and all AEs will be listed.

Drug-related TEAE (ADR) is defined as TEAE having the causal relationship of "*treatment-related*" with study drugs. In this trial, the definition of "*treatment-related*" is as follows: It refers to the relationship with the study drugs: related, possibly related, and unassessable. If the relationship between the AE and the study drugs is missing, the AE will be considered as an ADR.

AEs will be ranked from high to low according to the proportion of SOC/Cluster occurrence (total populations receiving the treatment), from high to low according to the proportion of PT under SOC (total populations receiving the treatment), and in alphabetical order if the incidences of at least 2 PTs are equal. If there is no AE under an SOC/Cluster or PT, the analysis will not be performed. Refer to Appendices 4 and 5 for the definition of Cluster classification.

In AE summary table, AEs after study drug treatment are analyzed according to the population, and the frequency and proportion are used for statistical description. AEs will be summarized using descriptive statistics according to Hengrui's Statistical Analysis Reporting Standards, including but not limited to the following contents:

- Any TEAE
- Treatment-related TEAE
- Any TESAE
- Treatment-related TESAE
- Grade  $\geq 3$  TEAE according to CTCAE grading
- Grade  $\geq 3$  treatment-related TEAE according to CTCAE grading
- Any TEAE  $\geq 5\%$
- Treatment-related TEAE  $\geq 5\%$
- TEAE leading to SHR-1210 treatment discontinuation and interruption

- TEAE leading to apatinib treatment discontinuation, treatment interruption, and dose reduction
- TEAE leading to death
- TEAE of special interest (AESI, the preferred term for AE provided by medical monitor, see Appendix 2 for details; other Grade  $\geq 3$  immune-related adverse events (irAEs): meeting irAE definition requirements and Grade  $\geq 3$  according to CTCAE v4.03)

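### The SAP plans no CTCAE-graded summary of laboratory values, although the protocol's secondary safety endpoint calls for one, and its three-level shift table hides worsening within a level

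*SAP*

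**What the plan says.** Protocol 2.2.2, and the synopsis in the same words, lists as a secondary safety endpoint "Incidences and severities of adverse events (AEs) and serious adverse events (SAEs), laboratory abnormalities, as per NCI-CTCAE v4.03".

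SAP 4.2.2 says only that laboratory data will be collected. SAP 5.5.3 gives the analysis:

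- A shift table of "The worst grades (normal, abnormal without clinical significance, and abnormal with clinical significance) of baseline and post-baseline laboratory tests". The order is fixed: "Severity, in descending order: Abnormal with clinical significance, abnormal without clinical significance, normal, and not examined".
- For continuous tests, "the laboratory tests and changes from baseline values will be summarized by scheduled time point using descriptive statistics", with minimum and maximum among the statistics.
- Listings: "All laboratory measurements will be listed by subject ID, among which, abnormal values will be marked with H/L", with clinical significance indicated. Unplanned results are listed.

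CTCAE enters the SAP through adverse events. SAP 5.5.2 states: "All AEs are encoded by using MedDRA v24.0 and graded using NCI-CTCAE v4.03". SAP 5.5.3 does not mention CTCAE.

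**The concern.** The endpoint names a grading system that the laboratory analysis never applies. A programmer who follows SAP 5.5.3 to the letter will produce no table of how many patients reached each CTCAE grade for ALT, bilirubin, platelets or any other test, and none of how baseline grade moved to worst grade.

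The substitute scale is coarse where this population needs detail. Protocol 4.1 admits ALT and AST up to 3 × ULN, bilirubin up to 1.5 × ULN, AKP up to 2.5 × ULN and creatinine up to 1.5 × ULN, so abnormal baselines are allowed by design. Protocol 1.1 names raised transaminases, raised bilirubin and thrombocytopenia among the main adverse reactions to apatinib. Protocol 1.2.3 reports Grade 3 thrombocytopenia in several liver-cancer patients given the combination with apatinib 375 mg. What is at stake is whether laboratory toxicity can be read from the tables by severity and relative to where each patient started.

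**Working it through.** There is no stated figure to reproduce. The check compares what each scale can display, then asks whether the other planned outputs supply what is missing.

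**1. Upward shifts that each scale can show.** With *k* ordered levels, the lowest being normal, there are *k*(*k* − 1)/2 possible upward shifts, and (*k* − 1)(*k* − 2)/2 of them start from an abnormal level.

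| Scale | *k* | Upward shifts | From an abnormal level |
|---|---|---|---|
| SAP 5.5.3 | 3 | 3×2/2 = 3 | 2×1/2 = 1 |
| Protocol Appendix 4 liver bands (normal, 1, 2, 3–4) | 4 | 4×3/2 = 6 | 3×2/2 = 3 |
| Normal plus Grades 1–4 | 5 | 5×4/2 = 10 | 4×3/2 = 6 |

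The one SAP shift from an abnormal level runs from abnormal without clinical significance (NCS) to abnormal with clinical significance (CS). Nothing is visible within NCS or from CS upward.

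**2. An illustrative patient.** Baseline ALT is 2.5 × ULN, which entry allows. Protocol Appendix 4 places this in Grade 1 (up to 3 × ULN); its Grade 3–4 band is "AST or ALT > 5×ULN and/or T.bili>3×ULN". I assume that every post-baseline value below is coded CS.

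| Worst ALT (× ULN) | Appendix 4 band shift | SAP shift if baseline was CS | SAP shift if baseline was NCS |
|---|---|---|---|
| 3.5 | 1 → 2 | none | one step |
| 6 | 1 → 3–4 | none | one step |
| 25 | 1 → 3–4 | none | one step |

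Whichever way the baseline was coded, the SAP table gives the same entry for all three outcomes.

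**3. The other planned outputs.**

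- *By-visit summaries (SAP 5.5.3).* The maximum can expose one extreme value at a scheduled visit. It does not say how many patients reached a grade, or from what baseline. SAP 5.1.5 keeps unplanned time points out of by-visit safety summaries.
- *Listings.* They hold every value, with H/L and clinical significance, but no grade and no count.
- *CTCAE-graded treatment-emergent events (SAP 5.5.2).* These count "any adverse events (AEs) that are new or worse than those at baseline (before treatment) after initiation of the study drugs", so worsening is covered if it is reported as an event. Protocol 7.2.2 asks sites to record abnormalities that are clinically significant or that meet the AE/SAE definition.
- *Liver event of special interest (SAP 5.5.2).* It is relative to baseline, but it combines transaminase and bilirubin criteria and covers no haematology. SAP Appendix 2 maps it to a single reported term.
- *Selected events (SAP 5.5.2, Appendix 4).* Greatest grade is summarised for ALT, AST, bilirubin, creatinine and thyroid terms. No platelet, neutrophil or haemoglobin term is on the list.

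**4. Comparison inside the plan.** For ECG, SAP 5.5.5 pairs a shift table on the same three levels with numeric bands for the worst PR and QTcF values and their change from baseline. Laboratory data get no such companion. Protocol Table 1 already acts on ALT/AST grade in relation to baseline grade, so grading these values is part of trial conduct.

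**The case against.** A reader might infer three stronger things that the documents do not support.

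- *That the table cannot show worsening once a value is abnormal.* It can: NCS to CS is an ordered step. Only worsening within a level is lost, and only in the shift table.
- *That severe laboratory toxicity goes unreported by grade.* Protocol 8.1.1 makes worsening of a pre-existing laboratory abnormality an adverse event, with no clinical-significance condition in that item. SAP 5.5.2 grades all events by CTCAE and tabulates Grade 3 or higher. Much severe toxicity should therefore appear by grade through the event tables.
- *That the scale is each investigator's own judgement and varies between sites.* SAP 5.5.3 does not say who assigns clinical significance. This is a plausible inference, not a stated fact.

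The protocol is also loose on this point. Section 7.2.1 applies CTCAE to AEs and SAEs, section 7.2.2 on laboratory evaluation does not mention it, and section 11.5.4 asks only for the baseline and the worse on-treatment value. One could argue that the SAP follows those sections. The endpoint line, however, most naturally attaches CTCAE to laboratory abnormalities, and SAP 5.5.3 reduces the worst value to three categories.

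These objections narrow the point without removing it. The event route depends on a report being made, the by-visit route on scheduled visits, and neither yields a count of patients by baseline and worst laboratory grade.

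**Conclusion.** The point holds as a mismatch between a declared secondary safety endpoint and its planned analysis. SAP 5.5.3 provides no graded incidence and no grade shift table for laboratory values. Its three-level table shows 1 upward shift from an abnormal baseline, where Grades 1 to 4 would show 6.

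That ratio describes the resolution of the scale; it does not count patients. The documents do not say how many enrolled patients would be coded CS at baseline, so the practical size of the ceiling is unknown. The conclusion rests on reading the endpoint line as applying CTCAE to laboratory abnormalities, and on the entry limits permitting abnormal baselines.

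The matter should be corrected. It does not touch the primary ORR analysis or its decision rule, and it concerns descriptive safety output.

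**What to change.** In SAP 5.5.3:

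1. Derive the NCI-CTCAE v4.03 grade for each gradable test (liver, renal, haematology, coagulation) from the numeric result and the laboratory's reference limits.
2. Tabulate baseline grade against worst post-baseline grade, using unscheduled as well as scheduled results.
3. Report the number and percentage of patients with any-grade and with Grade 3 or higher abnormality, for the same populations as the other safety tables.
4. Keep the three-level table for tests without a CTCAE grade.

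No new data should be needed: numeric results are already summarised, and H/L marking implies that reference limits are held, though this should be confirmed. The cost is SAP wording and some standard programming. Reported Grade 3 or higher laboratory rates may look less favourable than the event tables alone would suggest.
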